4.1.2 RANDOMIZATION

A randomization schedule will determine the order of wear of lens A and lens B for the first and second month, for each participant. Participants will be randomized at the beginning of Visit 2 after eligibility has been confirmed during V1.

A randomization schedule will be generated by CORE's data management team and provided to the unmasked research assistant(s) for the study. It will be included in the final report. Study investigators will remain masked to the randomization schedule until the study is completed and the database is locked.

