4.4 SCHEDULED AND UNSCHEDULED VISITS

This study has a total of 5 study visits, including the screening and exit visits. They are as follows:

- Visit 1: Includes screening, baseline assessments, randomization and fitting of both study lenses
- Visit 2: Randomization & Dispense of study lens Pair #1 (this will be combined with Visit 1 if all eligibility criteria met at V1)
- Visit 3: 1-month follow up of study Pair #1, dispense of study Pair #2
- Visit 4: 1-month follow up of study Pair #2
- EXIT: Typically occurring immediately after Visit 4 unless participant discontinues early

The scheduled follow-up visits 3 and 4 may only take place when the participant attends wearing the study lenses for a minimum of 6 hours. If this is not the case, and the participant is not experiencing any problems with the lenses, the appointment will be rescheduled, ideally within the visit window.

Visits that fall outside of the specified visit windows will be designated as protocol deviations and at the end of the study, the data collected during protocol deviations will be assessed for their suitability to be included in the analysis population.

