8 DISCONTINUATION FROM THE STUDY

Participants may be discontinued at the discretion of the investigator or sponsor in consideration of participant safety or protocol compliance, or at discretion of the participant. Participants discontinued from a study will be reimbursed \$20 per hour for their active involvement in the study (including the initial screening visit). Upon discontinuing, a participant will be offered the

option of their data being withdrawn from future statistical analysis. The following is a list of possible reasons for discontinuation from the study:

- Screening failure: Participants will be discontinued if they do not meet the inclusion and exclusion criteria outlined in section 4.2.3.
- Unacceptable performance with products to be used in study: Participants may be discontinued if they are unable to achieve acceptable comfort and /or vision with the study products.
- Positive slit lamp finding: Participants may be permanently discontinued from the study depending on the severity of the condition and on the judgement of the investigator.
- Adverse event: If a participant experiences an adverse event during the study they may be discontinued based on the clinical judgement of the investigator.
- Symptoms: If the participant has persistent symptoms they may be discontinued based on the clinical judgement of the investigator.
- Disinterest, relocation or illness: The participant may choose to discontinue due to reasons within or beyond their control.
- Violation of protocol or non-compliance: The participant will be discontinued if they are unable or unwilling to follow the protocol specified visit schedules and/or study procedures.
- Instillation of topical ocular medication: The participant will be discontinued if they elect to use a topical ocular medication during the study unless that topical ocular medication is prescribed for a limited duration (less than two weeks) to treat a transient condition; in this case the participant may remain an active participant (at the discretion of the investigator) after stopping topical ocular medication following resolution of the ocular condition).
- Lost to follow-up: The participant will be discontinued if they cannot be contacted and do not return for a final exit visit, and if the investigator has made a reasonable effort to contact the participant for a final study visit.

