10 STATISTICAL ANALYSIS AND DATA MANAGEMENT

10.1 STATISTICAL ANALYSIS

Primary comparisons will be between study lenses (e.g. in-office subjective ratings of lens handling collected after 1 month).

All data will be analyzed by CORE at the University of Waterloo. Unmasked data analysis will be conducted using Statistica, SPSS or other appropriate software. Descriptive statistics will be provided on information regarding baseline variables (age, gender, refractive error distribution, etc.).

Table 7 lists the primary outcome variables and anticipated statistical procedures.

Table 7: Statistical procedures

Variable	Analysis	Statistical test
Subjective ratings	Descriptive and other statistics	Mean, Median*, Standard Deviation, Minimum, Maximum, Frequency count
	Effect of treatment on outcome variable within subjects (comparison between study days)	Wilcoxon matched pairs test
		Mean, Median*, Standard Deviation, Minimum, Maximum, Frequency count
		Wilcoxon matched pairs test

The critical alpha level for statistical significance will be set at 0.05, with no adjustments for multiple comparisons.

All participants who were evaluated will be included in the analysis, unless their removal is agreed by the sponsor due to protocol deviations and/or adverse events. In the event of missing data, individual data points will not extrapolated from the collected data.

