13.4.1 MAJOR PROTOCOL DEVIATIONS

Major protocol deviations may impact the research protocol, information consent document or other study materials, usually cannot be anticipated ahead of time and are often necessary to ensure the safety and welfare of the participants.

The following are examples of protocol deviations that must be reported to the ORE:

- Changes in procedures initiated to eliminate immediate risks/hazards to participants;
- Enrollment of participants outside the protocol inclusion/exclusion criteria whether agreed to or not by the sponsor;
- Medication / device / intervention errors (i.e. incorrect drug or dosage of drug / incorrect contact lens(es) dispensed / incorrect care system dispensed);
- Inadvertent deviation in specific research intervention procedures or timing of the research intervention which could impact upon the safety or efficacy of the study-related intervention or upon the experimental design;
- Information consent documentation violations: no documentation of informed consent; incorrect version of, or incomplete, informed consent documentation used.

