13.4.3 REPORTING AND DOCUMENTING PROTOCOL DEVIATIONS

Major protocol deviations must be reported to the ORE within 7 days of the deviation occurring (or its discovery) using the Protocol Deviation Report Form 107 (PDRF). Information from the PDRF is provided to the Clinical Research Ethics Committee (CREC) at the next monthly meeting.

All protocol deviations (major and minor) occurring during the study will be documented, reported to the sponsor and included in the final report.

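### Sections 10.1 and 4.4 allow participants or data to be left out of the only visible analysis set after randomisation, without requiring a masked, pre-lock decision or a result with them kept in.

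*Combined protocol and SAP*

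**What the plan says.** Section 10.1 (Statistical analysis) starts from inclusion of every evaluated participant and then makes one exception: "unless their removal is agreed by the sponsor due to protocol deviations and/or adverse events". It does not say which deviations or adverse events qualify, when removal is agreed, or what those agreeing to it may have seen. The same section states: "Unmasked data analysis will be conducted using Statistica, SPSS or other appropriate software".

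Section 4.4 (Scheduled and unscheduled visits) treats visits outside the window as protocol deviations and adds that "at the end of the study, the data collected during protocol deviations will be assessed for their suitability to be included in the analysis population".

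The provisions closest to a safeguard are these:

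- Section 4.1.2: "Study investigators will remain masked to the randomization schedule until the study is completed and the database is locked".
- Section 13.4.3: "All protocol deviations (major and minor) occurring during the study will be documented, reported to the sponsor and included in the final report".
- Section 8 requires discontinuations and their reasons to appear in the final report, and section 12 puts deviations in the status reports to the sponsor.

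Section 8 also offers a participant who discontinues the "option of their data being withdrawn from future statistical analysis". That is a separate matter and a legitimate reason for data to be absent.

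**The concern.** Deviations and adverse events are known only after lenses have been worn. An adverse event may be caused by one of the lenses, and a deviation such as a rescheduled visit or short wear may reflect how a lens performed. In this crossover, taking out one participant takes out a whole A-B pair from a target of 20. If whoever decides has seen the ratings and knows the order of wear, the choice of pairs can move the primary Wilcoxon comparison. With no full-set result alongside, a reader of the report could not tell whether it had.

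The group open to removal need not be tiny. Section 10.1 does not confine the ground to major deviations. The follow-up window in Table 3 is four days (days 28 to 31), and section 5 also monitors wearing schedule and the timing of ratings.

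**Working it through.** **Inputs from the protocol.** Section 4.2.1: SD of paired differences 1.02, difference 0.71, alpha 0.05, power 84%, 20 completers, up to 25 randomised. Section 3: a non-directional null hypothesis. Table 7: Wilcoxon matched pairs test.

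**1. The plan's own figure.** Standardised difference 0.71/1.02 = 0.696. Noncentrality 0.696 × √20 = 3.113. The two-sided 5% critical t on 19 df is 2.093. Power from the noncentral t is 83.95%, against 84% stated. The sample size reproduces and is not in question.

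**2. Do other sections close the gap?**

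| Section | What it provides | What it leaves open |
|---|---|---|
| 4.1.2 | Investigators masked to sequence until lock | Sponsor and analysts not mentioned; nobody masked to ratings |
| 4.4 | Out-of-window data assessed when the study ends | Whether before lock; by whom; on what criteria |
| 10.1 | Analysis is unmasked | Whether removals are settled before it starts |
| 10.2 | Sponsor receives anonymised data on request | No timing limit; no statement on sequence |
| 8, 12, 13.4.3 | Deviations and discontinuations reported | Disclosure only; does not fix the analysis set |

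No second analysis set is defined in the visible text.

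**3. Baseline error rate.** The exact signed-rank test with 20 pairs at two-sided 0.05 rejects when the smaller rank sum is 52 or less. The attained level is 2.42% in each direction, so 2 × 2.42 = 4.84% in total.

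**4. Illustration of selective removal.** Assumed: no true lens difference; differences normal with SD 1.02; 20 pairs; f participants flagged at random with respect to ratings; and whichever 0 to 3 of them most favours one chosen lens removed. The documents give no rate for f. Simulated results, which vary by about 0.1 point between runs:

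| Flagged (f) | Favoured direction | Total, two-sided | Other direction (difference) |
|---|---|---|---|
| 0 | 2.4% | 4.9% | 2.5% |
| 1 | 3.0% | 5.0% | 2.0% |
| 2 | 3.7% | 5.2% | 1.5% |
| 3 | 4.5% | 5.5% | 1.0% |
| 4 | 5.5% | 6.2% | 0.7% |
| 6 | 7.5% | 8.0% | 0.5% |

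The favoured-direction rate at f = 3 or 4 is 4.5/2.4 = 1.9 or 5.5/2.4 = 2.3 times its baseline. The total is 5.5/4.9 = 1.1 or 6.2/4.9 = 1.3 times its baseline, because removals that help one lens suppress false positives for the other.

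**5. Variants, favoured direction.** For f = 1/2/3/4/6, 25 pairs give 2.9/3.5/4.2/5.0/6.8%. Differences rounded to 0.5 steps, with ties, give 2.9/3.4/4.1/5.2/7.3% with 20 pairs. If removals are not chosen but correlate with the paired difference, 1/2/3 removals give 3.2/3.7/4.1% at correlation 0.25 and 4.0/5.8/7.3% at 0.5. At correlation 0 they give 2.5/2.4/2.2%, essentially the baseline.

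**6. Power with deviating pairs removed or kept.** True difference 0.71, 20 pairs, two-sided signed-rank test:

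| Deviating pairs | Removed | Kept, behave like the rest | Kept, SD doubled | Kept, no lens difference |
|---|---|---|---|---|
| 1 | 80.0% | 82% | 78.5% | 77.4% |
| 2 | 77.5% | 82% | 75.4% | 72.2% |
| 3 | 73.5% | 82% | 71.6% | 66.5% |

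With three such pairs, keeping them gains 82 − 73.5 = 8.5 points at best and loses 73.5 − 66.5 = 7 points at worst.

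**The case against.** The best defence is that the text is silent rather than adverse. The default is inclusion. Sponsor agreement can be read as a second check on removals raised by a site whose investigators are masked to sequence. An assessment when the study ends is compatible with a review before lock, since section 4.1.2 names completion and lock separately. The statement that analysis is unmasked does not say when removals are settled. The cited SOPs, including the one on clinical data management, are not available and may hold a procedure. All of this stands, and it limits the point to a missing requirement.

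The adverse-event ground is also narrow. Someone who stops before rating both lenses has no pair to analyse whatever the clause says, so it matters only for those who had an event and still rated both.

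A reader might infer that the trial's false-positive rate would roughly double. The figures do not support that. Doubling applies to one direction only. It needs 3 or 4 flagged completers and a decision-maker who knows both ratings and sequence and picks the most favourable subset. Against the non-directional null of section 3, the total rises much less.

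A reader might also infer that the clause should simply be deleted and every deviating rating kept in the primary set. That goes further than the defect requires. The outcome is defined at one month within a day 28 to 31 window, and a rating taken well outside it may not measure that outcome. Whether keeping such ratings helps or costs power is not known (step 6).

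The objection does not supply the two missing requirements. Reporting that deviations occurred does not show what the result would have been with those participants kept in.

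**Conclusion.** The concern holds as a gap in the rule. Sections 10.1 and 4.4 permit post-randomisation removal of participants or data from the only visible analysis set. Nothing visible requires the decision to be masked and made before lock, or a full-set result to be shown.

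The possible size, under the assumptions of step 4, is a favoured-direction rate of 3.0% to 7.5% against 2.4%, and a total rate of 5.0% to 8.0% against 4.9%, for 1 to 6 flagged participants. The documents do not show where in that range the trial would fall, or that flagged participants rate handling differently. They do not say that the sponsor will see the sequence early or that removals will be made unmasked, so no finding of actual bias follows.

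The design and sample size are unaffected. The wording should be changed before the database is locked, because the primary result should not depend on a decision whose timing and masking are left open.

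**What to change.** Amend sections 10.1 and 4.4 to state three things:

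1. Every removal of a participant, or of out-of-window data, is decided and documented with reasons before database lock and unmasking, by people who have seen neither the ratings nor the lens sequence.
2. The primary comparison is reported for all randomised participants with removal-handling ratings for both lenses, alongside any result with exclusions. The only absences from this full set are participants who withdraw their data under section 8 and those with no valid A-B pair because of a dispensing error (section 13.4.1, "incorrect contact lens(es) dispensed").
3. Which of the two results is primary is named in advance.

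If an SOP already sets such a procedure, a sentence citing it in section 10.1 would meet the first item.

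The cost is a few sentences, one masked review before lock and one extra Wilcoxon test, with no new data and no change to the sample size. The downside is that the two results may differ and both must be shown, which is why the third item is needed. The full set remains complete-case, and participants may still withdraw their data.

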10.2 DATA MANAGEMENT

Data from this study will be retained by CORE for a minimum of 25 years on a password-protected server. After 25 years, data will be disposed of in accordance with the guidelines laid out by the University of Waterloo. More details regarding storage procedures are provided in CORE SOP014 Clinical data management.

CORE will provide a copy of the anonymized study data to the sponsor when requested. Data will typically be sent using a secure file share system operated by the University of Waterloo called Sendit which uses 128bit (or 256bit) SSL encryption. This system provides a secure way to transfer files when email is not appropriate, whether because of file size, file type or concerns over security. Sendit includes features such as password protection, a restricted time period for download, IP logging and email notification of download. Files may be encrypted prior to transmission at the request of the sponsor. Using this method means that data files are only stored on University of Waterloo servers during the transfer.

10.3 COMMENTS ON SOURCE DOCUMENTS

Data analysis will not be conducted on comments which have been recorded in the source documents. Only highlighted comments will be entered into the study database. Only relevant and applicable comments will be included in the final report as deemed necessary by the lead investigator.

11 PROTOCOL TRAINING

All study personnel will be required to complete training prior to their involvement in the study. Records of training will be kept at CORE.

12 STUDY MONITORING

Status reports will be provided to the study sponsor by email on a regular basis.

Status reports will include:

- The number of participants enrolled (i.e. assigned a study ID number), screened, dispensed, discontinued and completed.
- Details of protocol deviations.
- Reports of unintended events.

Study monitoring will be conducted by CORE personnel. Consent documentation will be reviewed by a person not involved in the consent process. To improve data integrity, data entry will be conducted by one person and a second person will visually compare the data entry to the source documents. All adverse events and protocol deviations will be reviewed by the Lead Investigator. All serious adverse events and major protocol deviations will be reviewed by the Principal Investigator.

13 STUDY MANAGEMENT

13.1 STATEMENT OF COMPLIANCE

This clinical study is designed to be in compliance with the ethical principles in the Declaration of Helsinki, with the ICH guidelines for Good Clinical Practice (GCP), with the University of Waterloo's Guidelines for Research with Human Participants and with the Tri-Council Policy Statement: Ethical Conduct for Research Involving Humans, 2nd Edition.

- Declaration of Helsinki
- ICH E6 - International Conference on Harmonisation; Good Clinical Practice

- <http://iris.uwaterloo.ca/ethics/human/guidelines/index.htm>
- <http://iris.uwaterloo.ca/ethics/human/ethicsReview/UWStatement.htm>
- <http://www.pre.ethics.qc.ca/eng/policy-politique/initiatives/tcps2-eptc2/Default/>

13.2 ETHICS REVIEW

This protocol will be submitted to and reviewed through the Office of Research Ethics (ORE) at the University of Waterloo. Notification of ethics clearance of the application is required prior to the commencement of the study.

13.3 CLINICAL TRIAL REGISTRATION

The sponsor will register this study with clinicaltrials.gov in accordance with section 801 of the Food and Drug Administration (FDA) Act which mandates the registration of certain clinical trials of drugs and medical devices.

13.4 PROTOCOL DEVIATIONS

Protocol deviations are unanticipated or unintentional changes to a study after it has received prior sponsor approval and ethics clearance. Protocol deviations can be major or minor.

13.4.1 MAJOR PROTOCOL DEVIATIONS

Major protocol deviations may impact the research protocol, information consent document or other study materials, usually cannot be anticipated ahead of time and are often necessary to ensure the safety and welfare of the participants.

The following are examples of protocol deviations that must be reported to the ORE:

- Changes in procedures initiated to eliminate immediate risks/hazards to participants;
- Enrollment of participants outside the protocol inclusion/exclusion criteria whether agreed to or not by the sponsor;
- Medication / device / intervention errors (i.e. incorrect drug or dosage of drug / incorrect contact lens(es) dispensed / incorrect care system dispensed);
- Inadvertent deviation in specific research intervention procedures or timing of the research intervention which could impact upon the safety or efficacy of the study-related intervention or upon the experimental design;
- Information consent documentation violations: no documentation of informed consent; incorrect version of, or incomplete, informed consent documentation used.

13.4.2 MINOR PROTOCOL DEVIATIONS

Protocol deviations caused by or which originate with research participants are considered minor, and normally are not reported to the ORE unless these result in increased risk to the participant(s). The following are examples of protocol deviations that are considered minor and do not require reporting to the ORE:

- Logistical or administrative aspects of the study (e.g., study participant missed appointment, change in appointment date);
- Inadvertent deviation in specific research intervention procedures or timing of the research intervention which would not impact upon the safety or efficacy of the study-related intervention or upon the experimental design (i.e., missing a measurement during a session that is not considered critical for the study).

13.4.3 REPORTING AND DOCUMENTING PROTOCOL DEVIATIONS

Major protocol deviations must be reported to the ORE within 7 days of the deviation occurring (or its discovery) using the Protocol Deviation Report Form 107 (PDRF). Information from the PDRF is provided to the Clinical Research Ethics Committee (CREC) at the next monthly meeting.

All protocol deviations (major and minor) occurring during the study will be documented, reported to the sponsor and included in the final report.

13.5 PREMATURE TERMINATION OF THE STUDY

The sponsor, CORE or the Office of Research Ethics at the University of Waterloo may terminate the study at any time for any reason.

13.6 STUDY PARTICIPANT RECORDS

Study participant records will be completed to comply with GCP guidelines. Records will contain:

- Unique study acronym and/or code;
- Participant ID;
- Date enrolled;
- Confirmation by investigator that participant met eligibility criteria;
- Confirmation that participant received a signed and dated copy of informed consent;
- Exit date;
- Investigator's signature confirming study exit.

13.7 RETENTION OF STUDY RECORDS AND DATA

Records and data from this study will be retained for a minimum of 25 years. Details regarding storage procedures are given in CORE SOP014 Clinical data management.

14 REPORT

A report will be sent to the sponsors according to terms described in the study contract.
